18.6 Missing Date Information for Adverse Events

18.6.1 Incomplete Start Date

Follow same rules as in Section [18.5.1](#).

18.6.2 Incomplete Stop Date

Follow same rules as in Section [18.5.2](#).

18.7 Missing Severity Assessment for Adverse Events

If the severity is missing for an AE starting on or after the date of the dose of the investigational product, then a severity of “Severe” will be assigned. If the severity is missing for an AE began before the date of the first dose of investigational product, then a severity of “Mild” will be assigned. The imputed values for severity assessment will be used for incidence summaries, while the actual values will be used in data listings.

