6.10.1 Recording of Angioedema Attacks

During the observation period and both treatment periods, parents/caregivers will use the eDiary each day to record any symptoms or occurrences of an angioedema attack experienced by the subject. The Investigator will complete a separate angioedema attack eCRF for each attack based upon their review of the data in the eDiary and include:

- Characterization of whether swelling or pain is (indicate all that apply):
 - Mucosal (pharyngeal, laryngeal, gastrointestinal, genitourinary)
 - Non-mucosal (truncal, external, facial)
- Location (site) of the swelling or pain (indicate all that apply):
 - Upper airway (includes laryngeal or pharyngeal)
NOTE: pharyngeal or oral swelling that results in airway compromise will be classified as a laryngeal attack
 - Gastrointestinal/abdominal (including symptoms of pain, nausea, vomiting, swelling, and/or change in bowel habits)
 - Genitourinary (including scrotum or vulva)
 - Facial
 - Extremity or peripheral (e.g., buttocks, external head/neck, trunk)

- Severity (intensity) of the sign/symptom at each location listed:
 - None
 - Mild: the angioedema attack sign/symptom(s) is noticeable but is easily tolerated by the subject and does not interfere with routine activities.
 - Moderate: angioedema attack sign/symptom(s) interferes with the subject's ability to attend school or participate in family life and social/recreational activities.
 - Severe: the angioedema attack sign/symptom(s) significantly limits the subject's ability to attend school or participate in family life and social/recreational activities.
- Angioedema attack trigger(s)
- Answer the question, “Was treatment administered for the attack?” If yes, record treatment administered.

In addition to recording the above information, study personnel will report any angioedema attack that occurs after the first dose of study drug as an AE (see Section 9.0).

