9.0 ADVERSE EVENTS

An AE is any untoward, undesired, unplanned clinical event in the form of signs, symptoms, disease, or laboratory or physiological observations occurring in a subject participating in a clinical study with study drug, regardless of causal relationship. An AE includes any condition that (1) was not present prior to study therapy but appeared following initiation of study therapy or (2) was present prior to study therapy, but worsened in severity and/or frequency following initiation of study therapy. **NOTE:** In this study, angioedema attacks after the first dose of study drug will be reported as AEs.

Adverse events will be monitored from the first dose of study drug in Treatment Period 1 through 1-week post-treatment. The Investigator will follow a subject with any AE until the event is either resolved or assessed as stable and, where appropriate, additional written reports

will be provided. The Investigator will evaluate and report the onset date, outcome, end date, duration (if <24 hours), severity (intensity), relationship to study drug, actions taken, and determination of seriousness for each AE. In addition, the Investigator will report if the AE onset occurred during study drug administration or within 24 hours following completion of study drug administration.

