9.1 Severity (Intensity) Assessment

The severity (intensity) of AEs will be assessed according to the following definitions:

- **Mild:** The AE is noticeable to the subject but is easily tolerated and does not interfere with routine activity. The AE may or may not require medication therapy or other therapy.
- **Moderate:** The AE interferes with routine activity but usually responds to medication therapy or other therapy.
- **Severe:** The AE significantly limits the subject's ability to perform routine activities and may not respond to medication therapy or other therapy.

If the intensity of an AE changes over time, the maximum intensity experienced should be recorded.

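### SAP 18.7 would count an attack graded mild or moderate on its own form as a severe TEAE if the AE severity field is left blank

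*SAP*

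**What the plan says.** Protocol 6.10.1 requires a dedicated form for each attack: "The Investigator will complete a separate angioedema attack eCRF for each attack based upon their review of the data in the eDiary and include" several items, among them "Severity (intensity) of the sign/symptom at each location listed", on a scale of none, mild, moderate and severe. The same section adds that "study personnel will report any angioedema attack that occurs after the first dose of study drug as an AE". Protocol 9.0 repeats this: "In this study, angioedema attacks after the first dose of study drug will be reported as AEs". AE severity is then graded on the scale in Protocol 9.1.

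SAP 18.7 states the imputation rule. Its condition is "If the severity is missing for an AE starting on or after the date of the dose of the investigational product", and the value assigned is Severe. On where that value is used, it says: "The imputed values for severity assessment will be used for incidence summaries, while the actual values will be used in data listings".

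SAP 11.1 reports severe TEAEs by treatment, both as children and as event counts, and tabulates TEAEs by maximum severity. It does not exclude attacks. SAP 10.3 derives the maximum severity of each attack, coded 1 to 3, for Cumulative Attack Severity.

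**The concern.** Worst-case imputation is meant for a value nobody knows. For an attack, an Investigator-completed grade of the same episode should normally be in the database, and SAP 18.7 does not send the analyst to it. One report could then show a single attack as mild in the efficacy data, blank in the AE listing and severe in the AE summary (Table 4.2.1) and the maximum-severity table (Table 4.3.1.1).

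There is no placebo arm. The safety comparison is 500 U against 1000 U in about 12 children, so a few misgraded events can alter how the severe-TEAE row reads. Attacks are also the primary efficacy outcome, so misgrading them affects a safety table through events that measure efficacy.

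**Working it through.** The plan states no figure for missing AE severity, for severe TEAEs or for attacks by dose, so there is nothing to reproduce. The check has two parts.

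**1. Does the rule reach a graded attack?** Take an attack in a treatment period, graded mild at every location on its eCRF, with the AE severity field blank.
- Efficacy (SAP 10.3): maximum severity is mild, score 1.
- Safety summaries (SAP 18.7 and 11.1): the AE starts after dosing and its severity is missing, so it is tabulated as Severe.
- AE listing (SAP 18.7): the blank is shown.

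So the rule does reach it. A moderate attack gives the same conflict with score 2. An attack graded severe is unaffected.

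**2. How large, and in which direction?** One child out of 12 is 1/12 = 8.3 percentage points, assuming all 12 receive both doses. At the administrative look at six children (SAP 14) it is 1/6 = 16.7 points; Tables 4.2.1 and 4.3.1.1 are flagged for that output. These are upper limits per child: a child who already has a severe TEAE at that dose adds nothing.

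Let L be attacks per child in a period, s the share of attacks that are truly severe, and q the probability that AE severity stays missing. All three are assumptions. For scale, Protocol 1.1.2 cites 6.3 attacks per 12 weeks on the drug in the earlier double-blind prevention study. Protocol Table 4 gives 0.35 per month at ages 6 to 11 in the open-label study, or 0.35 × 84/30.4 = 0.97 per 12 weeks.

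With 12 children and independent attacks:
- Added false severe events = 12 × L × (1−s) × q
- Added children with a severe attack AE = 12 × {(1−s)^L − [(1−s)(1−q)]^L}

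| L at the two doses | s | q | Added events | Added children |
|---|---|---|---|---|
| any | any | 0 | 0 vs 0 | 0 vs 0 |
| 1 vs 2 | 0.2 | 5% | 0.48 vs 0.96 | 0.48 vs 0.75 |
| 3 vs 6 | 0.2 | 2% | 0.58 vs 1.15 | 0.36 vs 0.36 |
| 3 vs 6 | 0.2 | 5% | 1.44 vs 2.88 | 0.88 vs 0.83 |
| 3 vs 6 | 0.4 | 5% | 1.08 vs 2.16 | 0.37 vs 0.15 |

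For example, in the fourth row the children are 12 × 0.512 × (1 − 0.857) = 0.88 and 12 × 0.262 × (1 − 0.735) = 0.83.

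With q and s equal at both doses, added events follow the number of attacks. The ratio of severe attack events between doses does not change, because both are multiplied by s + (1−s)q; only the absolute difference grows. If q differs by dose the order can reverse: L = 1, q = 10% against L = 2, q = 4%, with s = 0.2, gives 0.96 vs 0.77 events. It can also reverse if s differs: L = 1, s = 0.1 against L = 2, s = 0.6, with q = 5%, gives 0.54 vs 0.48. For children, the table shows either order even with equal q and s.

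**The case against.** The strongest case for leaving the rule alone has four parts.

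- Severity is a required item for every AE (Protocol 9.0), and edit checks, manual review and site queries follow (Protocol 11.0). Few blanks should reach database lock with 12 children. This stands, and it limits the practical size. But SAP 18.7 exists only for the blanks that survive.
- Worst-case imputation is a conservative convention, matched by SAP 18.8 for causality. This stands for AEs with no other source. It is weaker where the same episode has been graded elsewhere.
- The two scales differ. Protocol 9.1 defines mild as "The AE is noticeable to the subject but is easily tolerated and does not interfere with routine activity", close to the attack form, but its moderate and severe grades add response to therapy, which the attack form does not use. This stands: the attack grade is a close proxy, not the missing AE value. It would be wrong to say that the rule overwrites a recorded AE severity.
- The effect can be traced. The AE listing keeps the blank, Listing 6.2 shows each attack, and Table 4.3.1.1 splits by preferred term. This also stands, though the overall severe-TEAE row in Table 4.2.1 does not separate attacks.

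A reader might go further and infer that the rule inflates severe TEAEs most at the less effective dose, or that twice the attacks means about twice the falsely severe children. The second inference comes from the chance of at least one imputed attack, 1 − (1−q)^L, which is 14% at L = 3 and 26% at L = 6 for q = 5%. That counts children who already have a truly severe attack, and they add nothing to the row. The documents fix neither the missingness nor the severity mix by dose, so they do not support either inference.

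**Conclusion.** The point holds as a minor gap. As written, SAP 18.7 can contradict the Investigator's grade of the same attack, and nothing in the SAP prevents it. The size depends wholly on how many attack AEs lack severity after queries, for which the documents give no figure.

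A dose direction can be claimed only for absolute event counts, in expectation, and only if missingness and severity mix are the same at both doses. None can be claimed for the number or percentage of children. Nor is the rule the main reason that poor efficacy could look like a safety signal: that follows from the protocol's explicit decision to report attacks as AEs, and SAP 18.7 changes only their grade. Table 4.2.5 is affected too, but it compares quartiles of weight-adjusted dose rather than the two doses directly.

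**What to change.** Add to SAP 18.7: for an AE that is an angioedema attack, fill missing AE severity with the maximum severity on the matching attack eCRF; assign Severe only if that is also missing; and footnote the number of imputed severities by dose in each affected table.

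The fallback is needed. TEAEs run to 7 days after the last dose (SAP 11.1), whereas attack recording covers the observation and treatment periods (Protocol 6.10.1), plus follow-up of an attack ongoing at Visit 24b (Schedule 3). An attack starting after that window may have an AE record but no attack form.

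The cost is one sentence and a merge of the AE and attack data, which needs a matching key such as child and onset date. The price in interpretation is using a proxy scale, which the footnote should state. If no AE severity is missing, no result changes.

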18.8 Missing Relationship to Investigation Product for Adverse Events

If the relationship to investigational product is missing for an AE starting on or after the date of the dose of the investigational product, a causality of “Related” will be assigned. The imputed values for relationship to the investigational product will be used for incidence summaries, while the actual values will be presented in data listings.

18.9 Character Values of Clinical Laboratory Variables

Not applicable.

